# 4.5. Outcomes for the pilot cluster RCT

Table 2 Pilot cluster RCT outcomes

[figure not shown]
Measure	Description	Time point	
Primary			
Activities of daily living (ADL) assessed with the Disability Assessment for Dementia (DAD)	The DAD is a standardised instrument measuring the functional ability of PWD in activities of daily living (ADLs) [16]. It is 40-item scale regarding the subject's involvement in ADL. Seventeen items address basic ADL (hygiene, dressing, continence, and eating), and 23 items relate to instrumental ADL (meal preparation, telephoning, going on an outing, finance and correspondence, medications, and leisure and housework). Items can be categorised as part of initiation, planning and organization, and effective performance subscales, with the total score used most frequently, as is proposed as the primary outcome. Non-applicable items (e.g., those that a patient did not participate in even before the onset of their illness) are excluded from scoring, with the final scores being converted to a percentage. Scores thus have a potential range from 0 to 100%, with higher percentage scores representing greater competence in ADL. It will be completed at baseline and 6 months.	Baseline, 6 months	
	Each item can be scored:		
	1 point = Yes		
	0 point = No		
	or non-applicable = N/A.		
	A total score is obtained by adding the rating for each question and converting this total score out of 100. The items rated as N/A are not considered for the total score. For example:		
	A score of 33 on 40 (maximum score) converted out of 100 = 82.5%		
	A score of 33 on 38 (max. score with 2 N/A) converted out of 100=86.8%		
	This will result in a final score, a percentage which provides an appreciation of global function in ADL. Higher scores represent less disability in ADL while lower scores indicate more dysfunction.		
Secondary			
Patient participants			
European Quality of Life Instrument (EQ-5D-5L)	The EQ-5D-5L is a standardised instrument used to measure generic health-related quality of life [17]. It will be completed at baseline and 6 months by PWD with the capacity to complete the items.	Baseline, 6 months	

Quality of Life - Alzheimer's Disease (QOL-AD)	The QOL-AD is a standardised instrument for measuring quality of life for PWD [18, 19]. It is a 13-item scale administered via an interview. It includes the domains of physical condition, mood, memory, functional abilities, interpersonal relationships, ability to participate in meaningful activities, financial situation, and global assessments of self as a whole and QOL as a whole. It will be completed at baseline and 6 months by PWD with the capacity to complete the items.  Points are assigned to each item as follows: poor (1), fair (2), good (3), and excellent (4).  The total score is the sum of all 13 items.	Baseline, 6 months
International short form Falls Efficiency Scale (Short-FES-I)	The psychological consequences of falling will be determined using the Short-FES-I [20]. This is a 7-item measure of falls efficacy (or fear of falling). It will be completed at baseline and 6 months by PWD with the capacity to complete the items.  Points are assigned to each item as follows: not at	Baseline, 6 months
	all concerned (1), somewhat concerned (2), fairly concerned (3), and very concerned (4).  To calculate the Short FES-I score when all items are completed, simply add the scores for each item together to give a total that ranges as follows:	
	Short FES-I: minimum 7 (no concern about falling) to maximum 28 (severe concern about falling)	
	Scoring with missing items	
Time delle and On tool	If responses are missing on more than four items on more than two items (i.e.≥3) for Short-FES-I then the questionnaire scores cannot be used. If responses are missing on 2 or less on Short FES-I then it is possible to calculate a Short FES-I score. To do this first calculate the total score of the items which have been completed. Divide that score by the number of items completed and then multiply by 7. The new total score should be rounded up to the nearest whole number to give the score for an individual. For example, if scores on Short FES-I were: Item 1=2 Item 2=3 Item 3=missing Item 4=3 Item 5=2 Item 6=4 Item 7=missing Then 2+3+3+2+4=14/5 = 2.8×7= 19.6 which is rounded up to 20.	Describes
Timed Up and Go test	Patient participants stand up and walk 3 metres, turn around and walk back. The time taken to complete it is recorded. The test is scored as time in seconds.	Baseline, 6 months
	10 seconds or less = normal	
	10 to 20 seconds = good mobility	
	20 to 30 seconds = problems with mobility	

	A score of 14 or more seconds has been shown to indicate high risk of falls.	
Goal Attainment Scaling (GAS) (intervention only)	As part of the intervention, therapists will set individualised goals with participants. The goals will be agreed with the PWD by the therapists at the initial assessment and assigned 'weights'. GAS is a method of scoring the extent to which these goals are achieved in a way that is standardised for analysis [21, 22]. Progress towards goals will be measured at the final intervention visit, allowing a numerical score to be calculated at 6 months.	Baseline, 6 months
	Each goal is rated on a 5-point scale, with the degree of attainment captured for each goal area: If the patient achieves the expected level, this is scored at 0. If they achieve a better than expected outcome this is scored at: +1 (somewhat better)	
	+2 (much better)	
	If they achieve a worse than expected outcome this is scored at:	
	-1 (somewhat worse) or	
	-2 (much worse)	
	Goals may be weighted to take account of the relative importance of the goal to the individual, and/or the anticipated difficulty of achieving it.	
	Normally 3-4 goals are identified, which are incorporated into the single GAS score.	
	Overall Goal Attainment Scores are then calculated by applying a formula:	
	Overall GAS = 50 + $\frac{10 \Sigma(w_{i} x_{i})}{\sqrt{(0.7 \Sigma w_{i}^{2} + 0.3(\Sigma w_{i})^{2})}}$ Where:	
	wi = the weight assigned to the i th goal (if equal weights, wi = 1)	
	xi = the numerical value achieved (between -2 and + 2)	
	A simple spreadsheet calculator is available for use.	
Cognition assessed with mini ACE (Mini-ACE)	The Mini-ACE consists of 5 items and has a maximum score of 30	Baseline
Falls diary	Number of falls will be assessed through prospective completion of a diary during the 6 months of follow-up. Aid of an unpaid carer can be utilised if required. For each day, participants will be asked to record if they had any falls and, if so, explain the context and consequences of the fall. The data from the falls diary will be used to calculate the proportion of participants with one or more falls and the fall rate per person per year.	During the 6 months of follow up

Secondary		
Carer participants		
Carer burden assessed with the Zarit burden interview 12 (ZBI-12)	Carer burden will be measured using ZBI, a series of 12 questions designed to elicit the impact of the patient's disabilities on the life of the caregiver [23]. This will be completed with an informal carer at baseline and follow-up.	Baseline,
		6 months
	5-point scale from 0 to 4 Items.	
	Items 1 to 21: Never (0) to Nearly always (4)	
	Item 22: Not at all (0) to Extremely (4)	
	Total scores are calculated as a summation of the 12 items with a range from a possible 0 to 48. A higher score indicates a greater caregiver distress/burden.	
Carer participant quality of life assessed with the European Quality of Life Instrument (EQ-5D-5L)	The carer will assess their own HRQL using the EQ-5D-5L.	Baseline,
		6 months
Carer rated Patient participant quality of life assessed with the EQ-5D-5L proxy	The carer will assess the patient's HRQL using the Proxy version 2 of the EQ-5D-5L.	Baseline,
		6 months
Carer rated patient participant quality of life QoL-AD Proxy	The carer will assess the patient's HRQL using the Proxy version of the QOL-AD.	Baseline,
		6 months
Health and social care Utilisation Questionnaire (HUQ)	Data on the use of health, social care and wider resources will be collected via the HUQ.	Baseline, 3 months and
		6 months

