#### 6.2.1. **Inclusion criteria patient participants**

1. A diagnosis of dementia made prior to entry into the study. PWD must be on the Primary Care Quality Outcomes Framework (QOF) Dementia register.

Page 28 of 59

- 2. Must have sustained at least one fall within 6 months prior to identification as a potential study participant. A fall is defined as an event whereby a person comes to lie on the ground or another lower level with or without loss of consciousness.
- 3. Must be dwelling in their own home at the time of the index fall and returning to their own home at the time of the intervention.
- 4. Must have an unpaid carer available to assist with completion of the diaries.
- 5. Either has capacity to consent to participation, or a personal or nominated consultee who is able to give an opinion on the participation of the PWD.
- 6. Able to communicate in English
- 7. Aged over 50 years.

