#### 7.6. Baseline Assessments and Data

Baseline data for PWD and their informal carers consenting to the study will be collected by a clinical researcher within two weeks of confirmation of eligibility. For PWD, this will include the DAD, EQ-5D-5L, QOL-AD, Short-FES-I and Timed Up and Go test. GAS will be collected by the intervention therapist at baseline for those randomised to the intervention (Table 2). Informal carers will be asked to complete EQ-5D-5L proxy, QOL-AD proxy, HUQ, EQ-5D-5L and ZBI (Table 2).

After the baseline assessment, the clinical researcher will inform the central research team. If the participant is in the intervention arm, the referral will be sent to the intervention team using a structured referral form with details of the baseline assessment of the PWD and the unpaid carer. The intervention team will then arrange an initial intervention assessment within two weeks. If the participant is in the control arm, usual care will continue.

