Baseline data collected (see Table 2)	Х				
2 Assessment visits by Intervention team including Timed Up and Go Test		X			
Up to 22 visits by Intervention team			X		
Final visits will include Goal attainment scaling and Timed Up and Go test					
Completion of diary		X	X		
Completion of HUQ	X			X	X
Informed consent of professionals and participants and observation of interventions received		X	X		
Informed consent and qualitative interview with some professionals regarding views on intervention.			X		
Qualitative interview with patients, informal carers and professionals views on intervention (subset of participants who consent to qualitative study)			X		
Follow up outcome data collected					Х

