#### 8.2. Adverse events

#### 8.2.1. **Definitions**

Term	Definition	
Adverse Event (AE)	Any untoward medical occurrence in a participant to whom a medicinal product has been administered, including occurrences which are not necessarily caused by or related to that product.	
Serious Adverse Event (SAE)	
 
A serious adverse event is any untoward medical occurrence that:
 
results in death
 
is life-threatening
 
requires inpatient hospitalisation or prolongation of existing hospitalisation
 
results in persistent or significant disability/incapacity
 
consists of a congenital anomaly or birth defect
 
Other 'important medical events' may also be considered serious if they jeopardise the participant or require an intervention to prevent one of the above consequences.
 
NOTE: The term "life-threatening" in the definition of "serious" refers to an event in which the participant was at risk of death at the time of the event; it does not refer to an event which hypothetically might
 
	
Related and Unexpected SAE (RUSAE)	have caused death if it were more severe.  A related and unexpected SAE is an event which is related to the intervention; and 'unexpected' – that is, the type of event is not listed in the protocol as an expected occurrence.	

Table 4 Adverse Event definitions

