### Serious adverse events (SAE)

All deaths (from any cause) and hospitalisations due to falls, fractures or musculoskeletal injury will be recorded. Other SAEs will not be recorded or reported. Only related SAEs will be subject to expedited reporting.

Causality of reportable SAEs will be assessed by the site PI (or authorised delegate). All SAEs which are possibly, probably or definitely related to the intervention will be categorised as 'related'. If the PI or delegate is unable to assign causality within 24 hours of the site becoming aware of the event, the SAE will be treated cautiously and subjected to expedited reporting.

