#### Reporting procedure

- 1. If an adverse event is not classified as serious, no recording or reporting is required.
- 2. If an adverse event is classified as serious, but it is not a death or hospitalisation due to fall, fracture or musculoskeletal injury, no recording or reporting is required.
- 3. If the adverse event is serious, a death or hospitalisation due to fall, fracture or musculoskeletal injury, but not related to the intervention the Investigator must record the SAE on the CRF and no further reporting by site is required. The Exeter Clinical Trials Unit (ExeCTU) will report 3-monthly to the TMG, 6-monthly to the TSC and annually to the REC.
- 4. If the adverse event is serious, a death or hospitalisation due to fall, fracture or musculoskeletal injury, and related to the intervention the Investigator will report the SAE to ExeCTU within 24 hours of becoming aware of the event. ExeCTU will report to the sponsor within 24 hours of becoming aware of the event. If the event is death, the Sponsor or delegate will report to the TSC and REC within 7 days.

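### SAE causality is judged only against the intervention, so serious harm from a researcher-run Timed Up and Go at baseline, or at any control-arm visit, misses expedited reporting

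*Protocol*

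**What the plan says.** **The test.** Protocol Table 2 (section 4.5) schedules the Timed Up and Go at baseline and 6 months: "Patient participants stand up and walk 3 metres, turn around and walk back". It also notes that "A score of 14 or more seconds has been shown to indicate high risk of falls". Section 7.6 names the test in the baseline set, and says that these data "will be collected by a clinical researcher within two weeks of confirmation of eligibility". Section 7.7 sends the clinical researcher back to both arms for a second visit. SAP section 5.1 and Table 12 report the test by arm at baseline and 28 weeks. The participants are recent fallers by definition; inclusion criterion 2 in section 6.2.1 reads "Must have sustained at least one fall within 6 months prior to identification as a potential study participant".

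Therapists run the same test inside the intervention. Table 3 lists, for week 1, "2 Assessment visits by Intervention team including Timed Up and Go Test", and the test appears again at the final intervention visits.

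**The causality rules.** Table 4 (section 8.2.1) defines a RUSAE thus: "A related and unexpected SAE is an event which is related to the intervention". Section 8.3 says "All SAEs which are possibly, probably or definitely related to the intervention will be categorised as" related, and only related SAEs are expedited. The possible, probable and definite grades are all worded against the trial intervention, and the RUSAE paragraph covers deaths related to the intervention. In the reporting procedure, step 3 covers an event that is serious and of a recordable type, "but not related to the intervention the Investigator must record the SAE on the CRF and no further reporting by site is required". Step 4 is the expedited route for the same types of event when related to the intervention.

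**The concern.** A timed stand-and-walk test in recent fallers carries some risk of a fall. When the researcher runs it to collect outcome data, that risk comes from taking part in the research, whichever arm the participant is in. The safety section has no category for this. The list of potential risks in section 3.1 mentions injury from the intervention's physical activity, but not from outcome assessments.

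At stake is how fast serious harm caused by a trial procedure reaches the trials unit, the sponsor and, if fatal, the TSC and REC. The rule also treats like events differently. A fracture admission after the therapist's week-1 test can be expedited, while the same admission after the researcher's baseline test is not, and the protocol gives no reason for the difference.

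**Working it through.** The protocol states no figure for this point. The check sets the rules beside the visits and then counts tests.

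**Step 1: can an event at each test be related?**

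| Test | Exposure to the intervention | Can it be related as written? |
|---|---|---|
| Researcher, baseline, both arms | None: referral to the intervention team follows baseline (7.3, 7.6) | No |
| Researcher, follow-up, control arm | None: usual care only (7.3) | No |
| Researcher, follow-up, intervention arm | Intervention received | Arguable: a PI could grade it possible |
| Therapist, week 1 and final visits | The test is part of the intervention | Yes |

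**Step 2: what each route delivers (section 8.3, reporting procedure).**

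| Recipient | Step 4, related | Step 3, not related |
|---|---|---|
| Trials unit | Within 24 hours of site awareness | CRF entry only |
| Sponsor | Within a further 24 hours | No expedited notice |
| TMG | Not stated in this step | Every 3 months |
| TSC | Within 7 days if fatal | Every 6 months |
| REC | Within 7 days if fatal | Every year |

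The intervals in the last column are the times between reports, so they are upper limits on the wait for the next one.

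**Step 3: number of tests affected.** Inputs from section 9.1: 60 participants, 30 per arm, and the 80% follow-up used there to illustrate precision. I assume that everyone does the baseline test and that follow-up is the same in both arms.

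- Baseline, both arms: 30 + 30 = 60.
- Control follow-up: 0.80 × 30 = 24.
- Affected: 60 + 24 = 84.
- Intervention-arm follow-up, if the researcher repeats the test there: 0.80 × 30 = 24.
- All researcher-run tests: 84 + 24 = 108, so 84/108 = 78% are affected.

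With 70% follow-up (the green-light threshold) the affected count is 60 + 21 = 81. With 100% it is 60 + 30 = 90.

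The count of 84 does not depend on who runs the final test in the intervention arm. That matters because section 7.7 says that most, not all, measures are repeated, and Table 3 also gives a final test to the intervention team. Control participants have no intervention team, so the 28-week control column of SAP Table 12 can be filled only from the researcher's visit.

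**Step 4: do other clauses rescue the event?** Section 8.3 expedites an event whose causality cannot be assigned within 24 hours. A fall plainly caused by the test, in someone who has had no intervention, is not such a case. The not-assessable grade needs insufficient evidence, which does not fit either. Under section 8.4 the chief investigator may upgrade causality at the monthly review, but against the same intervention-only definition.

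**The case against.** The strongest reply is that the grades do not force an unrelated label. The not-related grade speaks of an incompatible relationship, or of other treatments, chemicals or disease as the explanation, and a fall during a research test is none of the last three. On this view the text is silent, and a cautious PI might leave causality unassigned and so trigger expedited reporting. Part of this stands: the protocol never says how to grade such an event, and a careful PI might find a way round. But where no intervention has been given, a causal link to it is incompatible, and steps 3 and 4 offer only two routes. Prompt reporting should not depend on a PI setting the definition aside.

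The second reply is that the harm would still be seen, and this stands. Section 8.3 records every death and every admission of the listed kinds, in both arms. The chief investigator reviews SAEs monthly, the TSC looks for patterns (8.4), a subset of the TMG meets at least monthly, and urgent safety measures (8.7) do not depend on relatedness. A reader might infer that the trial could go on injuring people without the sponsor or TSC ever being told. The documents do not support that.

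Two further inferences also fail. A reader might think that a non-fatal fracture loses a 7-day notice to the TSC and REC, but step 4 gives that notice only for deaths. (Table 4 read with section 8.5 might extend it to an unlisted related event; that is a separate ambiguity.) A reader might also think that the comparison of related harms by arm is distorted because the control count must be zero. SAP section 5.6 plans no such comparison: it reports all collected harms, in total and by group as treated.

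**Conclusion.** The gap is real and narrow. As written, a recordable SAE caused by a researcher-run Timed Up and Go at baseline in either arm, or at a control-arm visit, cannot be related. It takes step 3 and loses the 24-hour notice to the trials unit, the further 24-hour notice to the sponsor and, if fatal, the 7-day notice to the TSC and REC. About 84 planned tests are affected at 80% follow-up (81 to 90 for follow-up of 70% to 100%). That is a count of exposures, not of expected harms: the documents give no event rate, and it is probably low. At intervention-arm follow-up a PI could still choose possible, so it would be too strong to say that every researcher-run test is affected.

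The conclusion rests on protocol version 3.0 (08/11/2023). The SAP cites version 5.0 (May 2024), so whether the wording persists there must be checked. The case for changing it is that the correction costs almost nothing, the participants are vulnerable, and the pilot's procedures are meant to carry into a full trial.

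**What to change.** In Table 4 (section 8.2.1) and throughout section 8.3 (the SAE and RUSAE paragraphs, the causality grades from not related to definite, and reporting steps 3 and 4), extend relatedness to the intervention or to any trial procedure, including researcher-run outcome assessments. State that this applies in both arms. Add one field to the SAE form recording whether the event is attributed to the intervention, a trial procedure or neither. First check whether version 5.0 already does this.

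The cost is a wording amendment, one form field and a short note to sites. A few more events may be expedited. No test, visit, treatment, sample size or planned analysis changes.

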# 5. Study schema

Page 26 of 59

# 6. Study design

The study is a multi-centre, pilot cluster RCT of a rehabilitation programme intervention with embedded qualitative process evaluation. The PWD who have had a fall in the last six months are the patient participants; unpaid family members or friends of the patient participant are the carer participants. Patient participants and carer participants will be recruited in pairs, undertake the intervention, receive follow-up assessment at 28 weeks post-baseline assessment for the control group and 26 weeks after the initial assessment for the intervention group. The point at which followup assessment occurs varies between the control and intervention groups due to the assessment visits taking place for the intervention group during week 1 (see table 3). Each study site (cluster) will be randomly allocated to receive either the intervention or usual care. The intervention will include an assessment to identify any actions which need to be carried out to reduce the risk of falling or improve independence. This will be followed by a 12 week programme of activities facilitated by a team of therapists. Additional (booster) sessions will take place up to 6 months. The activities will be targeted at achieving personal goals chosen by the participants. We will follow participants up at 6 months to measure their independence in daily activities, mobility, fear of falling, falls, whether they achieved their goals, quality of life, caregiver burden and the health services and care they required. At the end of the trial we will know whether we should carry out a full trial to assess whether the intervention works and is good value for money.

